6.2 PREPARATION/HANDLING/STORAGE/ACCOUNTABILITY

6.2.1 ACQUISITION AND ACCOUNTABILITY

The investigator is responsible for ensuring adequate accountability of all study drug.

Accountability records will be provided to each study site or sites may utilize their own accountability records in order to:

- · Record the date received and quantity of study drug kits
- Record the date, subject number, subject initials, the study drug kit number dispensed
- Record the date, quantity of used and unused study drug returned, along with the initials of the person recording the information
- Study drug should be retrieved from each subject at the end of each dispensing interval. The
 quantity of study drug and the date returned by the subject should be reconciled against the
 Subject Dosing Diaries and recorded in the study drug accountability records. All study drug
 returned by the subject should be retained for review by the study site monitor prior to
 destruction.

Unused study drug may be destroyed at the site if the site has the appropriate standard operating procedure (SOP) in place. The study monitor will evaluate each study center's study drug disposal procedures and provide appropriate instruction for destruction of unused study drug supplies, as needed. If the site is unable to destroy unused study drug on site, the Sponsor will provide instruction for the return of the study drug for disposal/destruction.

6.2.2 FORMULATION, APPEARANCE, PACKAGING, AND LABELING

ZN-c5 will be supplied (and labeled per local regulation) as plain-faced capsules containing 25 mg (white size 4 capsules) or 100 mg (opaque white size 0) of ZN-c5. Please see the Pharmacy Manual for additional details.

Palbociclib (IBRANCE®, Pfizer Inc.) will be supplied (and labeled per local regulation) for the study.

6.2.3 PRODUCT STORAGE AND STABILITY

ZN-c5 capsules should be stored under refrigeration (2°-8°C or 36°-46°F) and protected from light. Storage conditions are specified on the label. The study center will be required to maintain a log of regular temperature readings in the storage area for the duration of the study.

Palbociclib capsules should be stored at controlled room temperature (15–30°C, 59–86°F) in their original container. Please see the most recent local or US Full Prescribing Information for additional information.

Until dispensed to the subjects, all bottles of study drug should be stored in a securely locked area, accessible only to authorized site personnel. To ensure the stability and proper identification, the drug product should not be stored in a container other than the container in which it was supplied. Appropriate precautions should be followed to avoid direct eye contact or exposure through inhalation when handling ZN-c5 capsules.

6.2.4 PREPARATION

Not applicable.

6.3 MEASURES TO MINIMIZE BIAS: RANDOMIZATION AND BLINDING

Not applicable.

6.4 STUDY INTERVENTION COMPLIANCE

The investigator is responsible for ensuring the study is conducted in accordance with the procedures and evaluations described in this protocol.

Compliance will be described by dose level in terms of the proportion of study drug actually taken based on returned pill count relative to the amount that was dispensed (taking into account physician-prescribed modification and interruptions).

6.5 CONCOMITANT THERAPY

At Screening, all medications taken up to 30 days prior to the screening visit will be recorded on the eCRF. In addition, supportive therapies given during the course of the study (e.g. blood transfusion, growth factor) should be collected and recorded on the eCRF.

At each study visit, the site will capture any and all medications taken by the subject since the last visit or during the visit (as applicable).

6.5.1 PROPHYLACTIC MEDICATIONS AND THERAPY

Premenopausal and perimenopausal women must receive a gonadotropin-releasing hormone agonist starting at least 4 weeks prior to enrollment and repeated, as per the prescribing information of the product administered, for the duration of study treatment.

The use of the following is prohibited during Cycle 1 in dose escalation cohorts:

• Prophylactic hematopoietic growth factors (e.g., G-CSF, erythropoietin)

• Prophylactic blood product transfusions

After Cycle 1, use of these treatments should be dictated by clinical situation and discussed with the Sponsor prior to initiation (when possible).

6.5.2 USE OF CYP3A4 AND CYP2C9 INHIBITORS AND INDUCERS

The following are prohibited at any time during the study:

Moderate and strong CYP3A4 and CYP2C9 inhibitors

The following are prohibited at any time during the study and for 2 weeks (or 5 half-lives, whichever is shorter) prior to study drug administration:

Moderate and strong CYP3A4 and CYP2C9 inducers

Examples of moderate and strong CYP3A4 and CYP2C9 inhibitors and inducers are provided in Section 10.4.6.

6.5.3 USE OF OTHER INHIBITORS OR INDUCERS

The following are allowed but should be avoided if possible. If required, doses of these agents may be modified as outlined in the appropriate product insert

- Substrates of CYP2C8 and BCRP
- Substrates of CYP3A

Subjects receiving palbociclib should avoid grapefruit or grapefruit juice. In addition, subject who require coadministration of a strong CYP3A inhibitor may require a reduced dose of palbociclib (see the most recent local or US Full Prescribing Information for palbociclib).

6.5.4 ADDITIONAL PROHIBITED MEDICATIONS

In addition, the following treatments are prohibited during the duration of the time that subjects are on active therapy during the study period:

- Hormone replacement therapy, topical estrogens, megestrol acetate, and selective estrogen receptor modulators
- Drugs known to cause QT interval prolongation (see Section 10.4.1)

6.5.5 RESCUE MEDICINE

Medications required to treat study drug related adverse events may be used as appropriate at the discretion of the investigator. Unless required urgently for patient care, the investigator should discuss such medications with the study monitor prior to use.

7 STUDY INTERVENTION DISCONTINUATION AND PARTICIPANT DISCONTINUATION/WITHDRAWAL

7.1 DISCONTINUATION OF STUDY INTERVENTION

Discontinuation from investigational treatment does not mean discontinuation from the study, and remaining study procedures should be completed as indicated by the study protocol (unless withdrawal of consent by the subject).

Subjects should have an End of Treatment Administration Visit as soon as possible (within 7 days) after the decision is made to discontinue study treatment (Section 7.4).

Subjects will return or will be contacted for a Safety Follow-up Visit 30 days (± 7 days) after the last dose of ZN-c5 taken (Section 7.5).

Subjects without PD at the time of study drug discontinuation will continue to undergo a Disease Assessment Follow-up Visit every 12 weeks (± 7 days) (Section 7.6).

Subjects will be followed for survival and subsequent breast cancer therapies.

7.2 PARTICIPANT DISCONTINUATION/WITHDRAWAL FROM TREATMENT AND FROM THE STUDY

Subjects may be discontinued from the investigational treatment in the following situations:

- Documented progression of disease or clinical progression
- Death
- Investigator discretion
- Non-compliance with study drug or protocol
- Important protocol deviation
- Pregnancy
- Patient discretion
- Withdrawal of consent (subjects are free to withdraw participation at any time)
- Lost to follow-up
- Subjects incorrectly initiated on study treatment
- Intercurrent illness that would, in the judgment of the investigator, affect assessments of clinical status to a significant degree
- Unacceptable toxicity
- Liver testing abnormalities meeting Hy's Law criteria (See Section 10.4.7)
- Study termination by the Sponsor

Subjects who are withdrawn from the study but are evaluable will not be replaced. Any subject who is withdrawn and is not evaluable may be replaced to ensure a minimum number of evaluable patients.

Subjects may withdraw from any aspect of the voluntary exploratory research at any time, without prejudice to further treatment and independent of any decision concerning participation in other aspects of the study.

If there is strong evidence of clinical benefit and reasons to justify continuation of the study drug, even though treatment discontinuation criteria have been met, this decision must be reviewed with the Sponsor, and continuation of therapy may be allowed assuming all other treatment resumption criteria have been met.

Subjects will be discontinued from the study in the following situations:

- Death
- Lost to follow-up
- Withdrawal of consent
- Study end per protocol
- Early study termination by Sponsor

7.3 LOST TO FOLLOW-UP

A participant may be considered lost to follow-up if they fail to return for 2 consecutive scheduled visits and is unable to be contacted by the study site staff.

The following actions must be taken if a participant fails to return to the clinic for a required study visit:

- Attempt to contact the participant and reschedule the missed visit
- Counsel the participant on the importance of maintaining the assigned visit schedule
- Ascertain if the participant wishes to and/or should continue in the study.

Prior to determining that a participant is lost to follow-up, the investigator or designee will make every effort to regain contact with the participant (e.g., at least 3 telephone calls and, if necessary, a certified letter to the participant's last known mailing address). Contact attempts should be documented in the participant's medical record or study file.

Participants who are unreachable based on the attempts outlined above will be considered to have withdrawn from the study with a primary reason of lost to follow-up.

If study drug is discontinued due to subject decision, the subject may elect to continue with treatment discontinuation assessments, safety follow-up and additional follow-up, if applicable.

7.4 END OF TREATMENT VISIT

At this visit, every effort should be made to perform the procedures listed in the Schedule of Activities for each study phase (Section 1.3).

7.5 SAFETY FOLLOW-UP VISIT

A Safety Follow-up Visit will be conducted 30 ± 7 days after the last administration of ZN-c5. If the subject begins a new anticancer treatment within 30 days of the last administration of study drug, the Safety Follow-up Visit should be performed prior to initiation of the new anticancer treatment, if possible

At this visit, every effort should be made to perform the procedures listed in the Schedule of Activities for each study phase (Section 1.3).

If the subject is unable to return to the study site, a follow-up phone call can be made by the study site to collect any new safety information that occurred during the Safety Follow-up Period.

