8.2.1.5 ADVERSE EVENTS

Subjects will be assessed for adverse events (AEs) per guidelines in the National Cancer Institute (NCI) CTCAE (Version 4.03) at the time points outlined in Section 1.3. Any non-serious AEs reported after initiation of ZN-c5 treatment on Cycle 1 Day 1 and throughout the study will be recorded on the eCRF with appropriate source documentation. The subject will be assessed for AEs until 30 days after the last dose of study drug, but prior to initiation of subsequent breast cancer therapy. Please refer to Section 10.4.4 for CTCAE grading criteria.

Please refer to Section 8.3.5 for additional information on AE reporting.

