8.3.4 TIME PERIOD AND FREQUENCY FOR EVENT ASSESSMENT AND FOLLOW-UP

The occurrence of an AE or SAE may come to the attention of study personnel during study visits, interviews of a study participant presenting for medical care, or upon review by a study monitor.

- The AE Reporting Period begins at the initiation of study medication (C1D1) and ends after the 30-Day Safety Follow-up Visit. All AEs should be followed up until resolution or until the AE is stable, if possible. Sponsor may request that certain AEs be followed beyond the protocol defined follow-up period.
- The SAE Reporting Period begins at the time a study participant signed an Informed Consent Form and ends after the 30-day Safety Follow-up Visit. Investigators are not obligated to actively seek SAEs after the 30-day period. However, if the investigator learns of any SAEs that occur after study participation has concluded and the event is deemed related to the use of study drug, he/she should promptly document and report the event to the study Sponsor. All SAEs will be followed until satisfactory resolution or until the site investigator deems the event to be chronic or the participant is stable. Other supporting documentation of the event may be

requested by the study Sponsor or designee (contract research organization [CRO]) and should be provided as soon as possible.

Note: Any medical condition that is present at the time that the participant is screened will be considered as baseline and not reported as an AE. However, if the study participant's condition deteriorates at any time during the study after Cycle 1 Day 1, it will be recorded as an AE.

All other untoward medical occurrences observed during the Screening period, including exacerbation or changes in medical history are to be captured on the medical history eCRF.

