8.4.3.2 DOSE ADJUSTMENT OF PALBOCICLIB

For subjects participating in the combination therapy portion of the study with toxicity potentially attributable to palbociclib, please follow safety and toxicity guidelines in the most recent local or US Full Prescribing Information for palbociclib (IBRANCE®, Pfizer Inc.).

Dose holds for reasons other than toxicity (e.g., scheduled surgery) are allowed for up to 21 days. Dose holds for reasons other than toxicity that last more than 21 days require that the subject be removed from study unless deemed in the best interest of the patient to continue and after discussion between the Investigator and the Sponsor's Medical Monitor (Section 7.2).

Unmanageable AEs attributed to palbociclib alone may result in continuation of single agent ZN-c5 therapy as long as none of the treatment discontinuation criteria are met (Section 7.2).

If treatment with ZN-c5 is discontinued, on-study treatment with palbociclib can be continued per protocol unless palbociclib is commercially available and treatment is reimbursed for the patient, then the patient can come off study treatment.

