9.4.4.2 ADVERSE EVENTS

All AEs will be listed. The focus of AE summary will be on treatment-emergent AEs. A treatment-emergent AE is defined as an AE that occurs or worsens in the period from the first dose of study drug to 30 days after the last dose of study drug.

AEs will be coded using the Medical Dictionary for Regulatory Activities (MedDRA https://www.meddra.org/) with descriptions by System Organ Class (SOC), High Level Group Term, High-Level Term, Preferred Term, and Lower-Level Term. The severity of AEs will be graded by the investigator according to the CTCAE, Version 4.03. The relationship of the AE to the IP will be categorized as related or unrelated.

TEAEs will be summarized by dose level. Summary tables will be presented to show the number of subjects reporting treatment-emergent AEs by severity grade and corresponding percentages. A subject who reports multiple treatment-emergent AEs within the same Preferred Term (or SOC) is counted only once for that Preferred Term (or SOC) using the worst severity grade. AE descriptions will be presented

by decreasing frequency for a given SOC and Preferred Term. Separate listings and summaries will be prepared for the following types of treatment-emergent AEs:

- Study drug-related AEs
- AEs that are Grade ≥ 3 in severity
- AEs leading to study drug interruption and/or dose modification
- AEs leading to study drug discontinuation
- SAEs

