3.6 Study Procedures

All subjects will be assessed by scheduled clinical, laboratory and other diagnostic assessments throughout the study. All efforts should be made to perform assessments as close as possible to the scheduled time points. Visit windows are provided below in [Table 2](#). Study assessments are to be performed as follows:

- Screening evaluations are to be performed within 28 days prior to first study drug dose.
- The day of first administration of study drug will be considered Day 1 of study.
- Cycle 1 Day 1, Cycle 1 Day 2, Cycle 1 Day 16 should be conducted on the day of, there is no window allowed. Cycle 1 Day 8 may be conducted \pm 1 day, Cycle 1 Day 15 may be conducted \pm 2 days.
- Day 1 evaluations for Cycles \geq 2 may be conducted \pm 4 days; Day 15 evaluations for Cycle 2 (only for subjects participating in Combination Therapy) may be conducted \pm 2 days. In the Combination Dose Escalation and Combination Phase 2 with palbociclib, the window for the Day 1 visit for subsequent cycles is only $+ 4$ days, since there must always be at least a full 7-day off treatment recovery period for palbociclib before starting the next 21-day dosing cycle.
- Tumor assessments should be performed every 8 weeks (\pm 7 days) after Cycle 1 Day 1 for the first 24 weeks. After 24 weeks, scans may be performed every 12 weeks (84 days) \pm 7 days, and at the time of discontinuation (if not performed within the last 4 weeks \pm 7 days).
- End of Treatment assessments should be performed within 7 days from discontinuation of study drug.
- Safety follow-up assessments should be performed 30 days \pm 7 days after the last administration of study drug, and prior to the start of new anticancer treatment.
- Disease assessment follow-up assessments should be conducted every 12 weeks (84 days) \pm 7 days for subjects without disease progression (PD) at the time of study drug discontinuation until confirmation of PD, initiation of the first subsequent anticancer therapy, withdrawal of consent, death, loss to follow-up or until the study is terminated, whichever occurs first. Survival follow-up should be conducted every 12 weeks (84 days) \pm 14 days from the time disease progression is confirmed or the first subsequent new breast cancer therapy is initiated.

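### The visit that closes AE and SAE reporting is timed from the last ZN-c5 dose, although combination subjects may continue study palbociclib after ZN-c5 stops; other sections use a different anchor, and the texts need reconciling.

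*Protocol*

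**What the plan says.** Three protocol provisions act together.

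- **Timing of the visit.** Section 7.5: "A Safety Follow-up Visit will be conducted 30 ± 7 days after the last administration of ZN-c5". Section 7.1 uses the same anchor: "Safety Follow-up Visit 30 days (± 7 days) after the last dose of ZN-c5 taken".
- **What the visit closes.** Under Section 8.3.4 the AE reporting period and the SAE reporting period both finish with the Safety Follow-up Visit. For SAEs, the period "ends after the 30-day Safety Follow-up Visit. Investigators are not obligated to actively seek SAEs after the 30-day period".
- **Dosing after ZN-c5 stops.** Section 8.4.3.2: "If treatment with ZN-c5 is discontinued, on-study treatment with palbociclib can be continued per protocol", except where palbociclib is commercially available and reimbursed, in which case the subject can come off study treatment.

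Other provisions use a different anchor.

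- Protocol 8.2.1.5: "The subject will be assessed for AEs until 30 days after the last dose of study drug".
- Schedule of Activities footnote 5 times the return visit from the last IP dose.
- SAP 3.6 places the safety follow-up assessments 30 ± 7 days "after the last administration of study drug, and prior to the start of new anticancer treatment".
- The TEAE definition in Protocol 9.4.4.2, repeated in SAP 6.6.3, covers events "in the period from the first dose of study drug to 30 days after the last dose of study drug". Protocol 9.4.4 sets the same limit for all safety data.

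The term study drug is not used consistently. SAP 6.6.2 counts palbociclib as a study drug and the synopsis lists it under Study Intervention. Protocol 10.4.5 attaches the term to ZN-c5 and names palbociclib separately.

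**The concern.** For monotherapy subjects the two anchors coincide. For a combination subject who discontinues ZN-c5 and stays on study palbociclib, they separate. A site that applies 7.1, 7.5 and 8.3.4 as written could hold the closing visit about a month after ZN-c5 stops, treat the reporting period as over, and no longer be obliged to look for SAEs in a subject who is still receiving study treatment.

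The analysis would not follow that rule. With palbociclib counted as a study drug, the safety and TEAE windows run to 30 days after its last dose. Time that the tables treat as observed would then include time in which collection may have ended. Any resulting error is an under-count of combination TEAEs, including the Grade ≥ 3 and serious summaries. Safety of the combination is a secondary objective in both the Combination Dose Escalation and the Combination Phase 2.

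**Working it through.** The plan gives no figure to reproduce. The check is a comparison of anchors and a day count.

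**Anchors for one combination subject who discontinues ZN-c5 and continues palbociclib**

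| Provision | Clock starts at | Palbociclib included? |
|---|---|---|
| Protocol 7.1, 7.5 (visit) | last ZN-c5 dose | no |
| Protocol 8.3.4 (end of AE/SAE reporting) | the Safety Follow-up Visit, so through 7.1 and 7.5 the last ZN-c5 dose | no, on that reading |
| Protocol 8.2.1.5 | last dose of study drug | depends on the term |
| Schedule footnote 5 | last IP dose | depends on the term |
| SAP 3.6 | last administration of study drug | yes, if 6.6.2 governs |
| Protocol 9.4.4, 9.4.4.2; SAP 6.6.3 (analysis windows) | last dose of study drug, plus 30 days | yes, if SAP 6.6.2 governs |

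The visit and reporting provisions therefore allow two different closing dates for the same subject.

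**Day count.** Inputs:

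- visit at 30 ± 7 days, so day V lies between 23 and 37 (Protocol 7.5);
- palbociclib 21 days on and 7 off in a 28-day cycle (Protocol 6.1.2.2);
- analysis window ending 30 days after the last study drug dose (Protocol 9.4.4.2).

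Assumptions: day 0 is the last ZN-c5 dose and falls on the last day of a cycle; palbociclib then runs for k full cycles without delay; palbociclib counts as study drug.

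- Last palbociclib dose: L = 28(k − 1) + 21.
- Time from the visit to the last palbociclib dose: L − V, or zero if negative. These are calendar days and can include days of the 7-day break.
- Part of the TEAE window after the visit: (L + 30) − V.

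For k = 2, palbociclib is taken on days 1–21 and 29–49, so L = 49 and the window ends on day 49 + 30 = 79.

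| Visit day V | Days to last palbociclib dose (49 − V) | TEAE-window days after visit (79 − V) |
|---|---|---|
| 23 | 26 | 56 |
| 30 | 19 | 49 |
| 37 | 12 | 42 |

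For k = 1, L = 21 comes before the earliest visit, so no treatment time is left uncovered. The window ends on day 51, which leaves 51 − 37 = 14 to 51 − 23 = 28 days of post-dose follow-up after the visit. Each cycle beyond the second adds 28 days to both columns. Stopping ZN-c5 on another day of the cycle moves L by less than 28 days.

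**The case against.** The best reply is that the protocol has other collection duties, and that a site would have to overlook several of them to stop recording events in a dosed subject.

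- Palbociclib is continued per protocol, and the Schedule of Activities has AE checks on Day 1 of every later cycle, at end of treatment and at the safety visit.
- Section 8.3.5 requires AEs arising on study to be documented whatever their relationship to treatment.
- Section 8.3.6 requires any SAE to reach the Sponsor within 24 hours of identification, related or not.
- Section 8.2.1.5 and footnote 5 point to the last dose of study drug or IP. Section 8.3.4 does not itself name ZN-c5, and 7.5 moves to the term study drug in its next sentence.
- After the reporting period, SAEs that the investigator learns of and considers related must still be reported (8.3.4).

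This stands in part. It defeats the stronger reading that collection definitely stops: early closure is one literal reading and not a settled rule. It does not remove the conflict. Section 8.3.4 is where the reporting periods are defined, and 7.1 and 7.5 both name ZN-c5. The late-reporting provision in 8.3.4 covers only related SAEs, so unrelated SAEs and non-serious AEs have no equivalent route there.

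A reader might also infer that the gap opens whenever ZN-c5 is modified for toxicity of unclear origin (8.4.3). It does not: a reduced dose is not a last dose, so only discontinuation starts the clock. Nor do the documents say that subjects who stop ZN-c5 first are mainly those who tolerated it poorly, so no selective bias of that kind can be asserted.

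**Conclusion.** The inconsistency is real and limited. Protocol 7.1, 7.5 and 8.3.4, read with 8.4.3.2, allow AE and SAE reporting to close while a combination subject is still taking study palbociclib. Protocol 8.2.1.5, footnote 5, SAP 3.6 and the analysis windows point to a later date.

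The two-cycle illustration, 12 to 26 days to the last palbociclib dose and 42 to 56 days of TEAE window, rests on the stated assumptions. The two ranges should be kept apart, because the second includes the 30-day period after dosing.

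The number of affected subjects is not given. The planned enrolment of about 40 in Combination Dose Escalation and about 112 in Combination Phase 2 might be taken as that number, but the documents do not support this. Only subjects who discontinue ZN-c5 and remain on study palbociclib count, some may leave study treatment under 8.4.3.2, and SAP 5.2 leaves open whether the Combination Phase 2 is carried out.

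The combination primary endpoints, Cycle 1 DLTs and CBR, do not depend on this visit. What is exposed is the completeness of secondary safety summaries.

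**What to change.** Reconcile Protocol 7.1, 7.5 and 8.3.4 with 8.2.1.5, Schedule footnote 5 and SAP 3.6 as follows.

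1. Time the Safety Follow-up Visit, and the end of AE and SAE reporting, from the last dose of whichever study drug is taken last, ZN-c5 or palbociclib.
2. Define study drug and IP as including palbociclib for this purpose, so that the collection rule and the Protocol 9.4.4 and SAP 6.6.3 windows share one end date.
3. In the SAP safety listings, flag any subject whose AE collection closed while palbociclib continued.

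This needs a few sentences, which could go in a clarification letter (SAP Section 8 records that one has already been issued), and one listing flag. No dose or treatment rule changes. The cost is a few later safety visits and some data queries. For subjects treated before the change, recovery of past events may be incomplete; the flag would show where.
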